15.2 Statistical analysis plan

A separate statistical plan including additional details about the statistical models, sensitivity analyses and mock tables will be finalised before unblinding and database lock.

15.2.1 Level of statistical significance

One interim analysis is planned once 100% of Australian sites have finished recruitment to the first 12-month intervention period.

Haybittle-Peto stopping rules will be used at the interim analysis using a difference of 3 standard-deviations on hospital mortality (or a p-value of 0.0027).

Given the conservative rule used and the negligible amount of type-I error rate spent at the interim analysis, the significance threshold will remain at 5% for the final analysis.

Final analyses of the primary outcome including sensitivity analyses will all be conducted using a two-sided significance level of 5%.

For the four secondary clinical outcomes, we will control the family-wise error rate by applying a Holm-Bonferroni correction.

No multiplicity correction will be applied to the ecology analyses or other statistical tests.

15.2.2 Timelines for analysis

The main primary analysis will be completed immediately after completion of the two intervention periods and the 3-month post-trial period when all RCT data and outcomes are available. This analysis will evaluate the primary outcome and clinical secondary outcomes.

A secondary analysis will occur after the completion of all data collection including uncensored hospital mortality and will analyse remaining secondary outcomes including ARO rates in both SDD and control groups in pre-trial, trial and post-trial periods.

15.2.3 Analysis of populations

Due to the cluster-crossover design, the group allocation for a patient is determined by the site and by the period during which they participated, regardless of treatment adherence.

The intention-to-treat analysis set will be used to assess both effectiveness and safety.

15.2.4 Analysis by region

SuDDICU is an international study conducted in two separate geographical regions – Australia and Canada/UK (as a combined region).

Due to an extended gap in recruitment timelines between Australia and Canada/UK due to operational and funding delays and interruption to recruitment caused by the SARS-coV-2 (COVID-19) pandemic in Canada/UK in 2020, a two-stage analysis of the dataset will be conducted:

- 1. The Australian database will be analysed as soon as the database is locked and reported as a separate analysis.
- 2. The Canadian / UK database will be analysed as soon as the database is locked and reported as a separate analysis
- 3. The Canada/UK database will be merged with the Australian database following database transfer from Sunnybrook Health Sciences Centre to the George Institute.
- 4. Indicative timelines for these analyses are 2021 and 2023 respectively.

15.2.5 Baseline analyses

Description of the cluster characteristics (e.g. location, size of ICU, baseline rates of antibiotic resistance) will be presented by treatment group.

Description of the baseline characteristics will be presented by treatment group.

15.2.6 Analysis of compliance and concomitant therapies

For patients in the SDD arm, the type of study antibiotic received, and the number of doses received each day between days 1-5.

The total number of doses received, the proportion of eligible doses delivered, as well as the number of days with at least one dose. This will be done separately for the SDD oral paste, SDD gastric suspension, SDD intervention intravenous antibiotics as well as non-SDD antibiotics.

For SDD intervention intravenous antibiotics the proportion of patients who received the full 4-day SDD course. We will report the number of daily defined doses of non- SDD antibiotics, and total antibiotics, received in the ICU between days 1-28 in the SDD and control arms in total and separately

15.3 Analysis of the Primary Outcome

The primary outcome is hospital mortality analysed as the proportion of patients who died during the index hospital admission (up to day 90).

The primary intervention effect will be estimated as the odds ratio (OR) of mortality between the SDD arm and the control arm obtained from a hierarchical logistic model including a random cluster effect and a random cluster-period effect.

Other analyses of hospital mortality will include a survival analysis of time to death obtained via a Cox model.

15.3.1 Adjusted analyses

The logistic regression model will be re-run after adjustment for the following individual baseline covariates:

- 1. Age (continuous)
- 2. Sex (male vs female)
- 3. Admission diagnosis (medical vs surgical)
- 4. Severity of illness (APACHE or MODS score) (continuous)

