15.1 Power calculation and sample size

The baseline mortality has been estimated from previous SDD studies in which a 30% hospital mortality for patients ventilated for more than 48-hours was observed in the control arm¹⁰. This was confirmed in our inception cohort pilot study where the observed mortality was 29.9% (95%CI 23.7 to 36.0%) and is consistent with the mortality of this cohort in other recent large intensive care trials.^{20,21} For the purposes of this trial we have estimated hospital mortality for our targeted patients of 29%.

The SuDDICU cRCT was originally designed to have 90% power to detect an in-hospital mortality difference of 3.5%, that is approximately half the 6% mortality difference seen in the SDD metaanalyses¹⁰ and the mortality difference observed in the most recent European SDD trial⁸. This absolute risk reduction is biologically plausible and consistent with the mortality difference seen in other large high-quality intensive care trials. The original design aimed to detect an absolute risk reduction in hospital mortality from 29% to 25.5% (3.5%), with 90% power, α < 0.05.

The inter-cluster correlation coefficient (ICC) is estimated to be 0.01. An ICC of 0.01 was observed for the previous Dutch cluster crossover study of SDD.⁷ An ICC of 0.01 has been calculated from the UK national Intensive Care National Audit and Research Centre and Australian and New Zealand Intensive Care Society Centre for Outcome Research databases.

Due to restrictions in funding in New Zealand, Canada and the UK, the original cCRT was modified to a x-cRCT conducted in Australia, assuming the same baseline mortality rate of 29% with 80% power and based on the inter-period correlation (IPC) coefficient estimated at 0.005 and sample size calculations are conservatively based on these assumptions. These assumptions are supported by data from the Australian and New Zealand Intensive Care Society ANZICS Clinical Trials Group x-cRCT PEPTIC study that reported an ICC 0.0093 and IPC 0.0072.²²

Once all sites are committed to the study, we will conduct a pre-specified validation analysis using ICC and IPC data available from the APD, for all ICU patients who either die or are ventilated for 48-hours or more, which approximates the inclusion criteria for this trial.

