The current SuDDICU x-cRCT will recruit 10 000 to 15 000 patients from 19 ICUs in Australia, 7 in Canada and 3 in the UK, each recruiting at least 150 patients per period (i.e. at least 300 patients per ICU).

An analysis consisting of Australian clusters only will have at least 80% power to detect an absolute reduction in mortality of 4.2%.

An analysis consisting of Canadian and UK clusters only will have at least 80% power to detect an absolute reduction in mortality of 5.5%.

The table below shows the detectable absolute risk reduction according to the number of clusters (ICUs) and numbers of patients recruited per period.

	Average number of patients recruited per cluster per period		
	150 patients	200 patients	250 patients
Australia only (20 clusters)	4.2%	4.0%	3.8%
Australia, Canada, UK (30 clusters)	3.5%	3.3%	3.1%
Canada and UK only (10 clusters)		5.5%	

Assuming that the main ecology analyses will be performed similarly to the mortality analysis, i.e. by comparing outcome data between groups during both intervention periods, the power can be calculated assuming a cross-over design.

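### The primary mortality model omits baseline covariates that the protocol already plans to adjust for in a re-run; making the adjusted model primary would add modest power and reduce exposure to measured case-mix differences.

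*Protocol*

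**What the plan says.** Protocol 15.3 defines the primary effect as an odds ratio from a "hierarchical logistic model including a random cluster effect and a random cluster-period effect". No patient characteristic is named in that model.

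Protocol 15.3.1 then states "The logistic regression model will be re-run after adjustment" for age, sex, medical versus surgical admission, and a continuous severity score that may be APACHE or MODS. Section 8.3 plans baseline collection of demographics, admission diagnosis and a routine severity score.

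On testing, 15.2.1 says "Final analyses of the primary outcome including sensitivity analyses will all be conducted using a two-sided significance level of 5" per cent. On power, 15.1 says "An analysis consisting of Australian clusters only will have at least 80% power to detect an absolute reduction in mortality of 4.2" per cent. Nothing in 15.1 allows for covariates. Section 15.5 uses available data in the primary analysis, without imputation.

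**The concern.** Patients are not individually randomised between an ICU's two periods. The trial is unblinded (7.6), ICUs learn their sequence in the pre-trial phase (7.1), and entry depends on a clinician's forecast of how long ventilation will last (6.3.1). In Canada, deferred consent to treatment is sought only in the intervention arm (12.5.3), and data are deleted if a withdrawing patient or substitute also refuses their use (7.8). Each of these is a route by which the patients analysed could differ between SDD and control periods.

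The crossover removes stable differences between ICUs. The random cluster-period term widens the standard error for ordinary period-to-period variation. Neither removes bias from a systematic difference in case mix between arms. Section 17.2 plans to confirm similar recruitment rates in the two kinds of period, but similar counts do not ensure similar severity.

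Two things are at stake: some power, and which analysis carries the headline if the two models disagree.

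**Working it through.** **Inputs from Protocol 15.1 and 15.2.1**
- Control mortality 29% ("For the purposes of this trial we have estimated hospital mortality for our targeted patients of 29" per cent)
- Within-period correlation 0.01 ("The inter-cluster correlation coefficient (ICC) is estimated to be 0.01")
- "inter-period correlation (IPC) coefficient estimated at 0.005"
- Cluster-period size m = 150 ("each recruiting at least 150 patients per period")
- Two-sided 5%
- 20 Australian clusters in the power table, 19 Australian ICUs in the text

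**Assumed, because the protocol gives no figure:** the share R² of patient-level outcome variance that the covariates explain, 0.11 to 0.20. In a logistic simulation at 29% mortality this corresponds to an AUC of about 0.70 to 0.78.

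**Step 1: reproduce the plan's figure.** The cluster-crossover design effect is

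DE = 1 + (m − 1)·ICC − m·IPC = 1 + 149 × 0.01 − 150 × 0.005 = 1.74.

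With 20 clusters, effective n per arm = 20 × 150 / 1.74 = 1,724. A two-proportion test of 29% against 24.8% has null SE √(2 × 0.269 × 0.731 / 1,724) = 0.01510 and alternative SE 0.01509. Power = Φ[(0.042 − 1.96 × 0.01510) / 0.01509] = Φ(0.82) = 79.4%, and the detectable difference at 80% power is 4.23 points. The stated 4.2 is reproduced without any covariate term.

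**Step 2: same calculation with the 19 ICUs in the text.** Effective n = 19 × 150 / 1.74 = 1,638 per arm. Power at 4.2 points is 77.4%; the detectable difference is 4.34 points.

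**Step 3: adjust, letting covariates explain patient-level variance only.**

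DE_adj = (1 − ICC)(1 − R²) + m(ICC − IPC) = 0.99(1 − R²) + 0.75.

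| R² (assumed) | DE | Equivalent gain in patients | Power at 4.2 points, 19 × 150 | Detectable difference |
|---|---|---|---|---|
| 0 | 1.74 | none | 77.4% | 4.34 |
| 0.11 | 1.63 | 1.74/1.63 = 7% | 80.0% | 4.20 |
| 0.16 | 1.58 | 1.74/1.58 = 10% | 81.2% | 4.14 |
| 0.20 | 1.54 | 1.74/1.54 = 13% | 82.1% | 4.09 |

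With the table's 20 clusters, power goes from 79.4% to 82.0% (R² 0.11) and 84.0% (R² 0.20). If case mix also explained part of the between-period variance, the gain would be larger; the protocol gives no basis for a value.

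**Step 4: where the gain comes from.** A patient-level logistic simulation (1,500 runs, 1,724 per arm, 29% against 24.8%, no clustering) gave:

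| Covariate slope per SD (AUC) | Log OR, unadjusted → adjusted | SE, unadjusted → adjusted | Power, unadjusted → adjusted |
|---|---|---|---|
| 0.8 (0.70) | −0.212 → −0.237 | 0.077 → 0.082 | 79% → 83% |
| 1.0 (0.74) | −0.213 → −0.251 | 0.077 → 0.084 | 81% → 86% |
| 1.25 (0.78) | −0.219 → −0.275 | 0.077 → 0.087 | 81% → 89% |

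The SE of the log OR rises. Power increases because the conditional log OR moves further from zero. Without clustering, all of the variance is open to adjustment, so these gains exceed those in Step 3; the simulation shows the mechanism and direction.

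**Step 5: sensitivity to case mix.** With slopes of 0.8 to 1.25, an assumed mean severity difference of 0.1 SD between arms shifts crude mortality by 1.5 to 2.1 points. Against the 4.2-point Australian target that is 1.5/4.2 = 36% to 2.1/4.2 = 50%. The 0.1 SD is illustrative; nothing in the protocol predicts an imbalance of that size, or any imbalance.

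**The case against.** The strongest reply is that nothing is misstated. An unadjusted primary with a prespecified adjusted re-run is accepted practice, the four covariates are named in advance, and the stated power is reproduced without them. The dispute is only over which of two planned analyses leads. All of that stands, and it limits the point to a recommendation.

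A reader might infer several stronger things that the documents do not support:

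- **That the plan has no protection against case mix.** It has the crossover, the cluster-period effect and the planned re-run, which would reveal a shift in the measured covariates.
- **That case mix does differ between periods.** The protocol supports only that it could.
- **That adjustment would remove selection bias.** It deals with measured covariates only.
- **That these are the four strongest predictors, held for every patient.** No section ranks predictors, 8.3 lists other risk factors, and collection is a plan.
- **That the odds ratio becomes more precise.** Its SE rises (Step 4).
- **That a standardised odds ratio leaves the effect measure unchanged.** The current primary is conditional on the random effects; a marginal odds ratio is a different quantity.

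Two practical objections also stand. Severity may be APACHE or MODS, and the protocol states no rule for combining them. Section 15.5 excludes imputation, so an adjusted primary could lose patients with a missing covariate. The fix has to deal with both, but neither is a reason to keep the unadjusted model as the lead.

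**Conclusion.** The point holds as a low-cost improvement, not as an error or contradiction. Leading with the unadjusted model gives up roughly 2.6 to 4.7 points of power at 19 × 150 (77.4% to 80.0-82.1%) and 0.14 to 0.25 points of detectable difference (4.34 to 4.20-4.09). It also leaves the headline more exposed to any measured case-mix difference between SDD and control periods.

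The size rests on an assumed R² of 0.11 to 0.20 acting on patient-level variance only, and on the protocol's ICC of 0.01 and IPC of 0.005. Weaker covariates would give less. The 77.4% starting point reflects 19 ICUs rather than the 20 in the power table; that discrepancy is a separate matter and is not caused by the absence of adjustment, although adjustment of this strength would about make it up.

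**What to change.** For each analysis not yet locked:

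1. In 15.3, make the covariate-adjusted hierarchical logistic model of 15.3.1 primary, with the same random effects, and keep the unadjusted model as a sensitivity analysis.
2. Report a standardised risk difference and marginal odds ratio beside the conditional odds ratio, and state that the marginal odds ratio is a different measure.
3. Put severity on a common footing, either by standardising within score type (APACHE or MODS) or by a score-by-type term. The planned re-run needs such a rule anyway.
4. Amend 15.5 to allow simple imputation of missing baseline covariates, so that no patient is dropped; outcome handling stays as it is.

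No new data are needed. The costs are a more model-dependent primary estimate, a small change to 15.5 and an added standardisation step. Timing also matters: 9.1 dates the Australian lock and analysis to October-December 2021, while 9.2 puts Canada/UK and the combined analysis in 2023. If one region is already locked, the regional reports would have different primary models. In that case, show both models in every report and say which was primary when that database was locked.

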15.4 Planned subgroup analyses

- 1. Nature of admission
 - i. Operative vs. non-operative
 - ii. Trauma vs. non-trauma

- 2. Severity of illness as determined by above vs. below median ICU admission APACHE II or MODS score
- 3. Sex: male vs. female

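### Section 15.4 examines effect modification by severity only through a median split of APACHE II or MODS; keeping the score continuous would be a cheap gain in power under a smooth gradient

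*Protocol*

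**What the plan says.** Protocol section 15.4 lists three subgroup factors: nature of admission (operative or not, trauma or not), severity and sex. The severity item reads "Severity of illness as determined by above vs. below median ICU admission APACHE II or MODS score". It gives no numeric cut, does not say which dataset supplies the median, and plans no analysis in which effect modification is examined on the full score.

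Section 15.3.1 uses severity differently in the adjusted model: "Severity of illness (APACHE or MODS score) (continuous"). Both sections allow either of two scoring systems.

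Section 15.2.4 has the regions analysed separately before merging. For the first region it says "The Australian database will be analysed as soon as the database is locked and reported as a separate analysis"; Canada/UK follows in the same way. Section 3.2.4 announces a third publication on the combined data, so there will be three reports.

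Section 15.1 gives detectable differences for the overall mortality comparison only. No power is claimed for any subgroup analysis.

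**The concern.** Admission type, trauma and sex are categories by nature. Severity is the one listed factor that has to be cut to make a subgroup, and the protocol gives no reason for cutting it. A median split treats a patient just above the median like the sickest patient in the trial, and a patient just below it like the least sick. If the benefit of SDD changes gradually with severity, the comparison of two halves discards much of the evidence for that change.

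What is at stake is a secondary question of clinical interest: does SDD work differently in sicker patients? With the split alone, a real gradient is more likely to be missed and then read as an absence of heterogeneity.

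**Working it through.** **Inputs from the protocol.** Two-sided 5% level (15.2.1); control mortality 29%, ICC 0.01 and inter-period correlation 0.005 (15.1); at least 150 patients per ICU per period, so at least 300 per ICU; 19 Australian ICUs and 29 in all. This gives 19 × 300 = 5,700 and 29 × 300 = 8,700 patients as minimum sizes.

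**Inputs that are assumed.** The protocol does not give the distribution of the score, the shape or size of the severity gradient, or the association of severity with death. The assumptions below are a standard normal score, a severity log-odds ratio of 0.8 per SD, an average treatment log-odds ratio of −0.177 (29% to 25.5%), and a linear gradient g per SD.

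**1. The plan's own figure.** For 20 clusters and 150 patients per cluster-period:
- Design effect = 1 + (m − 1)·ICC − m·IPC = 1 + 149 × 0.01 − 150 × 0.005 = 1.74.
- Effective patients per arm = 20 × 150 / 1.74 = 1,724.
- Detectable difference at 80% power = 4.23%; power at the stated 4.2% = 79.4%.

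The main-effect figure therefore reproduces. It says nothing about an interaction.

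**2. Information kept by the split.** For a normal score and a linear interaction, the efficiency of a median split is 2/π = 0.637. Equal power needs π/2 = 1.57 times the patients. With λ the expected z-value of the continuous test (1.960 plus the normal quantile of its power), power after the split = Φ(λ·√0.637 − 1.960). For 80% power, λ = 1.960 + 0.842 = 2.802, and 2.802 × 0.798 = 2.236, so the split gives Φ(0.276) = 61%.

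| Power, continuous | Power, split | Loss (points) |
|---|---|---|
| 30% | 20.8% | 9.2 |
| 50% | 34.6% | 15.4 |
| 70% | 50.9% | 19.1 |
| 80% | 60.8% | 19.2 |
| 90% | 73.4% | 16.6 |
| 95% | 82.0% | 13.0 |
| 99% | 92.8% | 6.2 |

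**3. Simulation.** Model: logit(p) = −0.95 + 0.8z − 0.177·arm + g·arm·z. The Wald test of arm × z was compared with the Wald test of arm × (z above the median). The rows for g = 0.15 to 0.20 use 2,000 trials each, with cluster and cluster-period effects at the protocol's ICC and IPC in the generated data. The rows for g = 0.10 use 600 trials without cluster effects.

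| Patients | g per SD | Continuous | Split | Loss (points) |
|---|---|---|---|---|
| 5,700 | 0.10 | 30% | 21% | 9 |
| 5,700 | 0.15 | 56% | 38% | 18 |
| 5,700 | 0.177 | 67% | 47% | 20 |
| 5,700 | 0.20 | 80% | 59% | 21 |
| 8,700 | 0.10 | 42% | 31% | 11 |
| 8,700 | 0.15 | 72% | 52% | 20 |
| 8,700 | 0.177 | 86% | 66% | 20 |
| 8,700 | 0.20 | 93% | 77% | 16 |

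A separate run with 800 trials per setting gave losses of 17 to 23 points for g = 0.15 to 0.20 at these sizes, 9 to 12 points at g = 0.10, and 10 to 21 points at 12,000 patients. One 600-trial run showed 24 points (8,700 patients, g = 0.15: 76% against 52%). With 2,000 trials the same setting gave 20, so the higher value is probably simulation noise.

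**4. Sensitivity to the assumptions.** At 80% continuous power the loss is about 12 points for a uniform score (efficiency 0.75) and about 31 for an exponential one (efficiency 0.48). If the true modification is a step at the median, the order reverses. With 6,000 patients and step effects of ±0.12 and ±0.18 on the log-odds scale, the split had 46% and 81% power against 31% and 63% for the continuous test, a gain of about 15 and 18 points.

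**The case against.** The strongest case on the other side has four parts.

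- **The size is not a property of the plan.** A reader might infer that the design forfeits a definite 17 to 24 points of power. The documents do not support that, because nothing in them fixes the gradient, its linearity or the score distribution. The gradients that give the largest losses are also strong. With an average log-odds ratio of −0.177, g = 0.15 puts the point of no effect at 0.177/0.15 = 1.18 SD and g = 0.20 at 0.89 SD, so about 12% and 19% of patients would be harmed. The combined sample may also reach the planned 10,000 to 15,000; at 15,000 the loss for g = 0.15 to 0.20 was about 6 to 17 points. This objection stands, and the figure is given only as a conditional range.
- **The cut is not shown to move.** A reader might also infer that the boundary changes between the three reports, so that one patient is above the median in one paper and below it in another. Section 15.4 says median without naming a dataset, and section 15.2 defers further detail to a separate analysis plan that was not available here. A moving cut is a natural inference, not something the protocol states. Australian and Canada/UK patients do not overlap, so reclassification could arise only between a regional report and the combined one.
- **Two scores complicate the remedy.** A single raw-score term, or one numeric cut carried across regions, fails if some sites use APACHE II and others MODS. This stands and shapes the fix.
- **There is no contradiction.** Continuous adjustment in 15.3.1 and grouped odds ratios in 15.4 serve different purposes. This is also correct.

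What remains is that the protocol itself chooses the split as its only look at severity, when a more informative analysis is available from the same data.

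**Conclusion.** The point holds as a minor improvement. Under a roughly normal score and a linear gradient on the log-odds scale, the split keeps about 64% of the interaction information. It costs about 10 to 23 points of power for gradients of 0.10 to 0.20 per SD with 5,700 to 12,000 patients, and less where power is already very low or very high. All of those conditions are assumptions, and a true step at the median would favour the split.

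The primary analysis, the sample size and every stated power figure are untouched.

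**What to change.** In section 15.4, item 2:

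- Base the severity test on a treatment-by-severity interaction with the score kept continuous, in the hierarchical logistic model of section 15.3.
- If both APACHE II and MODS are used, standardise the score within each scoring system, or analyse each score separately.
- Add a spline term as a check on linearity.
- Keep the above- and below-median odds ratios as descriptive display only, with one pre-specified cut per score used in all three reports and its source stated.

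The cost is a few lines of wording and somewhat more analysis work; no new data are needed. The downside is reliance on a linear gradient, which the spline check addresses. If the separate analysis plan already contains these elements, it is enough to align the protocol text with it.
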